Study protocol

NCT number: 05785130

Date of the document: 2 March 2023

Title: The Effects of White Noise for Adult Patients' Sleep Quality in Intensive Care Unit.

Background and objective: Sleep is one of the basic physiological needs for humans. According to the American National Sleep Foundation, the recommended sleep duration for adults (18-64 years old) is 7-9 hours per day, while for older adults (65 years and above), it is 7-8 hours per day (Hirshkowitz et al., 2015). However, sleep disturbances are common among intensive care unit (ICU) patients. It is estimated that more than half of ICU patients report experiencing sleep disorders during their stay (Blissitt, 2016). A study by McKinley et al. in 2012 tracked 164 critically ill patients, aged 18 and above, who were in the ICU for more than 48 hours and used a ventilator for more than 24 hours. The study found that one week after transferring out of the ICU, 50% of patients still reported moderate to severe sleep disturbances, and one-third continued to experience moderate to severe sleep disturbances 26 weeks after discharge. This indicates that sleep disorders not only occur during ICU admission but may also persist after discharge.

There are many factors contributing to sleep disorders in ICU patients,

including pain, light, and the severity of illness. Noise is one of the factors leading to sleep disturbances in critically ill patients (Pisani, 2015). According to the World Health Organization's recommendations, daytime environmental noise should be below 45 decibels, and nighttime sleep noise should be below 35 decibels (World Health Organization, 2010). However, ICUs are filled with the sounds of operating medical equipment and alarm signals due to treatment requirements. A study by Darbyshire & Young (2013) measured the noise levels in five adult ICUs and found that the noise level exceeded 45 decibels throughout the day, with the lowest noise level at 4 a.m. being 51 decibels, which is still higher than the WHO recommendation. Furthermore, noise levels exceeding 85 decibels occurred 16 times during the night. A 2007 study by Uğraş and Öztekin, which used a questionnaire to investigate the causes of sleep disturbances in patients in a neurosurgical ICU, found that 78.6% of the 84 patients reported sleep disturbances, and 57.6% of them attributed the disturbances to environmental noise. Sudden loud noises not only cause sleep interruptions but also increase the number of awakenings, leading to sleep disorders (Devlin et al., 2018; Reuter-Rice, 2020). Once sleep disturbances occur, they negatively affect the immune system, respiratory function, metabolic functions, and cardiovascular health, while also causing psychological stress and negative emotions (Reuter-Rice, 2020; Sterniczuk et

al., 2014). Over time, these disturbances affect the recovery of critically ill patients, leading to extended hospital stays, increased medical costs, and higher mortality rates (Altman et al., 2018; Pisani, 2015). Furthermore, sleep disorders can impair cognitive functions such as memory, attention, and reaction time, increasing the risk of delirium (Van et al., 2009). Thus, sleep issues in ICU patients require urgent attention.

Currently, the treatment of sleep disorders in ICU patients still primarily involves medication, but cognitive decline, drug tolerance, and drug dependence may lead to negative effects on sleep. Therefore, many international studies have explored non-pharmacological interventions to improve ICU patients' sleep, such as reducing light and noise stimuli, minimizing nighttime disturbances, or teaching relaxation techniques. Among these, white noise intervention is one approach to reduce light and sound stimulation. The purpose of white noise is to create a consistent sound with fixed frequencies and tones, which can raise the hearing threshold during nighttime sleep, reducing the frequency of being awakened by sudden loud noises, and thereby enhancing sleep quality through masking effects (Farokhnezhad Afshar et al., 2016).

White noise interventions have often used white or pink noise in research, typically targeting newborns, students, or healthy adults. For example, a study

on white noise in a cardiac ICU found that exposure to 40-50 decibel noise between 8-9 p.m. and 11 p.m.-12 a.m. for one hour each night for three days significantly improved sleep quality compared to the control group (Farokhnezhad Afshar et al., 2016). This suggests that the effectiveness of white noise interventions in improving ICU patients' sleep quality is inconsistent, possibly due to differences in the duration and timing of the intervention. Furthermore, sleep disturbances during the night in the ICU are unpredictable, and short intervention periods may not be sufficient to protect patients from sudden noise events that occur outside the intervention hours. Many studies on white noise in adult ICUs use the Pittsburgh Sleep Quality Index to measure sleep quality, which assesses sleep over the past month. However, since critically ill patients are in the acute phase and their ICU stay is usually short, the Pittsburgh Sleep Quality Index may not accurately reflect their sleep condition during their ICU stay. Additionally, individuals may have preferences for different types of white noise, making it difficult to standardize the type of noise used in interventions. Therefore, the purpose of this study is to explore the effectiveness of white noise interventions on sleep quality in adult ICU patients. The aim is to utilize this low-cost, easy-to-implement, and accessible measure to block out ICU noise and improve the sleep quality of critically ill patients in the ICU.

Method: The inclusion criteria of this study as follows: (a) age must be greater than or equal to 20 years old, (b) admitted to the ICU and have been intubated for at least 24 hours, (c) awareness of people, time, and place without hearing impairment., (d) be able to communicate in writing., (e) the Glasgow Coma Scale(GCS) score must be equal to or greater than 11(with a vocal response of 1 in the patient post-endotracheal tube placement). The exclusion criteria of this study as follows: (a) history of insomnia, Alzheimer's disease, or depression, (b) routine use of sedative-hypnotic drugs (opioids, benzodiazepines, non-benzodiazepines, antihistamines, and melatonin) before admission, (c) post-operation in the operating room before ICU admission, (d) intensive care delirium screening checklist(ICDSC) score of at least 4 or Confusion Assessment Method for the Intensive Care Unit (CAM-ICU) positive. *Sample:* The sample size for this study is calculated using G*Power 3.1, with an effect size set at 0.25 (Kotrlik & Williams, 2003), $\alpha = 0.05$, and power = 0.8. The minimum required sample size is 58 participants. In statistical analysis, a sample size of 30 is often considered the threshold for a large sample, the total sample size will be 60 participants, with 30 participants in the experimental group and 30 participants in the control group.

Study interventions

This study adopts a convenience sampling method and will be conducted

in the Fifth Department of Internal Medicine ICU at Kaohsiung Chang Gung Memorial Hospital. The study groups are set as follows: the white noise group will receive white noise intervention, while the conventional treatment group will receive standard care. The total sample size of 60 participants will be divided into 6 blocks of 10 participants each, with random assignment generated by a computer. Upon admission to the ICU, patients who meet the inclusion and exclusion criteria will be selected. The principal investigator will fully explain the study's purpose and procedures to the patients, and once informed consent is obtained, the recruitment process will begin. On the first day of enrollment, participants will complete a baseline assessment using the VAS sleep quality scale (T0). Random assignment will then allocate participants to either the Treat (white noise) group or the Control (standard care) group based on the generated block sequence.

For the white noise group, in addition to receiving standard care, white noise will be introduced from 11 p.m. to 6 a.m. the following morning. A noise-reducing sleep aid device will be placed at the corner of the bedside cabinet, and a decibel meter will be positioned near the patient's head. The volume of the noise-reducing sleep aid device will be controlled between 40-50 decibels. According to a study by Van et al. in 2009, up to 90% of delirium occurs on the third day of ICU admission, so the intervention will be applied

continuously for three nights. The control group will receive standard care. Both groups will complete the VAS sleep quality scale at 6 a.m. on the first day after intervention (T1), the third day (T2), and the fifth day (T3). The total number of assessments will be four, each taking approximately 5 minutes.

Outcome measurements: The Verran and Snyder-Halpern Sleep Scale (VSHSS) was initially developed by Snyder-Halpern & Verran in 1989 to measure the sleep quality of hospitalized patients from the previous night. The internal consistency reliability was found to be 0.82. The original scale consisted of four subscales: sleep fragmentation, sleep disturbance, effective sleep, and compensatory sleep. In 1996, Simpson et al. revised the scale to include three subscales: sleep disturbance, effective sleep, and compensatory sleep. Tranner et al. tested the scale in 2003 with 110 hospitalized and surgical patients, and the Cronbach's α values for the subscales of sleep disturbance, effective sleep, and compensatory sleep were 0.86, 0.80, and 0.63, respectively. In 2007, Fang and Wang translated this scale, and the Cronbach's α values for sleep disturbance, effective sleep, and compensatory sleep were 0.90, 0.72, and 0.64, respectively. The overall internal consistency was 0.84, and the Content Validity Index (CVI) was 1.0.

The scale consists of 15 items, each scored on a 0-100mm visual analog scale, where 0 represents the lowest score and 100 represents the highest. The

sleep disturbance section contains 7 items, with a total score range from 0 to 700. A lower score indicates more severe sleep disturbance. The effective sleep section contains 4 items, with a total score range from 0 to 400. A lower score indicates less effective sleep. The compensatory sleep section contains 4 items, with a total score range from 0 to 400. A lower score indicates a greater need for compensatory sleep. Since the original author of the scale has passed away, the version of the Verran and Snyder-Halpern Sleep Scale used in this study has been translated and authorized by the publisher.

Statistical Methods: Descriptive Statistics: Personal demographic data and disease characteristics of the study participants will be analyzed. Categorical variables will be presented as frequencies and percentages, while continuous variables will be expressed as means and standard deviations.

Inferential Statistics:Independent samples t-tests or chi-square tests will be used to compare the homogeneity of sleep quality and demographic data between the white noise group and the general care group before the intervention.

Independent samples t-tests will be used to compare the differences in sleep quality pre- and post-intervention between the white noise group and the general care group.

Generalized Estimating Equations (GEE) will be used to compare the

effects of the white noise group and the general care group under the factors of group, time, and the interaction between group and time.

Ethical considerations: Ensuring Non-Disclosure of Participants' Identity and Information: A research code will be used to represent each participant's identity during the study, ensuring that the participant's name, ID number, address, medical record number, or any other personal information will not be disclosed during the research process.

Confidentiality of Participant Data and Diagnosis: The research investigator will maintain confidentiality and carefully protect the privacy of participants' data. Before the study begins, participants will be informed that the questionnaires they complete and the data collected will be encoded and kept confidential, solely for the purposes of this study. These data will be securely stored in a locked cabinet by the principal investigator, and only the study team will have access to them. No external parties will have access to the data. After the study is completed, the data will be destroyed five years later and will not be retained. If at any point during the study a participant experiences discomfort, they have the right to withdraw at any time without affecting the treatment and rights they are entitled to.

Confidentiality in Publication of Results: If the study results are published, the identity of the participants will remain confidential. The researcher will

explain the study's purpose and procedures to participants before obtaining their consent and having them sign the informed consent form. In future academic publications, no identifying information such as the research institution or participant codes will be included.

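### The stated inputs (effect size 0.25, alpha 0.05, power 0.8) do not by themselves give 58 patients, and the 80% power is tied to neither planned analysis

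*Combined protocol and SAP*

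**What the plan says.** The Sample paragraph of the Method section reports a G*Power 3.1 calculation "with an effect size set at 0.25" (with a literature citation), alpha 0.05 and power 0.8, and concludes: "The minimum required sample size is 58 participants". The step to 60, 30 per arm, is justified by "In statistical analysis, a sample size of 30 is often considered the threshold for a large sample". The paragraph does not give the G*Power test, the effect metric, sidedness, the number of measurements, a within-patient correlation, a nonsphericity value or the score concerned.

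The Statistical Methods section plans two comparative analyses. The first is a t-test, with usual care as the comparator: "Independent samples t-tests will be used to compare the differences in sleep quality pre- and post-intervention between the white noise group". The second is a GEE with group, time and their interaction. Neither is called primary, and the sample-size paragraph refers to neither. Under Study interventions the plan says "The total number of assessments will be four, each taking approximately 5 minutes". The first of these is before allocation: "participants will complete a baseline assessment using the VAS sleep quality scale (T0). Random assignment will then allocate participants". Outcome measurements describes three subscales and does not single one out.

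**The concern.** A power figure means something only when it is attached to a test and to a size of effect on a defined score. Here a reader cannot tell which analysis has 80% power, or for what benefit. The first comparative analysis listed is a two-group t-test. Under either common reading of 0.25 (Cohen's d or Cohen's f), that test needs far more than 58 patients.

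What is at stake is interpretation. If 0.25 is the effect on the score the t-test analyses, 30 per arm would miss it in about 84% of trials (d) or 52% (f). A non-significant result could then be taken as 80%-powered evidence against a modest benefit, which the t-test would not support. The plan does not say that a null result will be read in this way; the present wording leaves the reading open.

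**Working it through.** **Inputs from the plan:** effect size 0.25, alpha 0.05, power 0.8, stated N = 58, planned 30 + 30, four assessments.

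**Assumed, because the plan is silent:** two-sided test, effect metric, correlations (equal between all visits), nonsphericity values. Repeated-measures ANOVA stands in for the GEE.

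**1. Does the t-test give 58?** With n per arm, power comes from the non-central t distribution with 2n − 2 degrees of freedom and noncentrality d√(n/2).

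- 0.25 read as Cohen's d: 253 per arm, **506** in total, for 80%. (The normal approximation, 2(1.960 + 0.842)²/0.25² ≈ 252 per arm, gives 504.)
- 0.25 read as Cohen's f: for two equal groups f = d/2, so d = 0.5. This needs 64 per arm, **128** in total.
- One-sided testing gives 398 or 102, so sidedness does not explain 58.
- 58 (29 per arm) is the two-sided size for d = 0.75.

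**2. What do 30 per arm give on the t-test?** √(30/2) = 3.873, and the critical t is 2.002.

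| Effect on analysed score | Noncentrality | Power |
|---|---|---|
| d = 0.25 | 0.968 | 15.9% |
| d = 0.5 | 1.936 | 47.8% |
| d = 0.736 | 2.850 | 80% |

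If 27 per arm are analysed (an assumed loss of 3 per arm), 80% is reached at about 0.78 SD.

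**3. Can the t-test reach 80% another way?** If the effect is 0.5 SD of the raw score and the t-test uses change from baseline, the standardised effect is 0.5/√(2(1 − ρ)). At ρ = 0.5 this is 0.5, with 47.8% power. At ρ = 0.7 power is 69%, and it crosses 80% at ρ about 0.77. No correlation is stated.

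**4. Can a repeated-measures calculation give 58?** For the group effect over m visits, λ = f²Nm/[1 + (m − 1)ρ], tested on F(1, N − 2), with f = 0.25.

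- m = 4, ρ = 0.25, N = 58: λ = 0.0625 × 58 × 4/1.75 = 8.29, power 80.8%. N = 56 gives 79.3%, so 58 is the minimum.
- m = 4, ρ = 0.5, N = 58: λ = 14.5/2.5 = 5.8, power 65.8%. The minimum is then **82**.
- m = 3: 58 at ρ about 0.15, and 86 at ρ = 0.5.

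For group-by-time, λ = f²Nmε/(1 − ρ). 58 also appears with two times at ρ about 0.12, and with four visits at ε = 0.7 and ρ = 0. With four visits under sphericity, power at N = 60 is 91% at ρ = 0 and higher at larger ρ. With three or two visits at ρ = 0 it is 85% or 77%.

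**5. What benefit would these settings imply?** T0 precedes randomisation, so no group difference is expected there.

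- Group effect, f = 0.25, four visits: the average difference is 2 × 0.25 = 0.5 SD. If it is zero at T0 and constant over T1–T3, it is 0.5 × 4/3 = 0.67 SD at each of those visits.
- Group-by-time, four visits, same profile: f = 0.2165d, so d = 0.25/0.2165 = 1.15 SD.

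The same 0.25 therefore stands for quite different benefits, depending on the G*Power option.

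**The case against.** The strongest reply is that 58 may be perfectly correct. The plan has four assessments and a GEE with a group factor. A four-visit group effect at f = 0.25 and correlation about 0.25 gives 58 exactly, so the fault would be incomplete reporting and not arithmetic. That stands. The effect size also carries a citation, whose content cannot be checked here and which may define the metric. That stands too, and it is why the t-test figures are given for both d and f. A citation still would not supply the test, number of visits, correlation or score.

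A reader might infer more from the gap than it supports:

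- **That 58 was miscalculated.** Several unstated combinations give it.
- **That 128 or 506 is the right sample size.** Each holds only if the t-test is the basis and 0.25 is the effect on the score it analyses.
- **That the GEE is underpowered.** At f = 0.25 the four-visit group-by-time test under sphericity has at least 91% power with 60 patients.

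It can also be said that the remedy should not presume the t-test was the basis. That is fair, and the fix below is conditional.

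**Conclusion.** The concern holds as a gap in the power statement. The three stated inputs do not determine 58, and the 80% is attached to no analysis. If 0.25 is the effect on the t-tested score, the 80% is not a property of that test: power with 30 per arm is about 16% (d) or 48% (f), against 80% at 0.74 SD.

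The t-test figures assume two-sided alpha 0.05, one score at one time point, and all 60 patients analysed. The repeated-measures figures also rest on assumed correlations, nonsphericity and ANOVA as a proxy for the GEE; they are examples, not bounds. It should be corrected, but it does not call for a larger trial.

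**What to change.** Keep 60 patients. Name the analysis and the score to which the power statement applies.

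**If it is the t-test,** replace the sentence with:

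> With 30 analysed per arm and two-sided alpha 0.05, the independent-samples t-test on one score at one time point has 80% power for a between-group difference of 0.74 SD of the analysed score.

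Add that this becomes about 0.78 SD if 27 per arm are analysed, marked as an assumed loss; Ethical considerations allows withdrawal at any time.

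**If it is the GEE,** state the G*Power option, effect metric, number of visits, correlation and nonsphericity value that give 58. Give the implied between-group difference in SD units, labelled as resting on the assumed correlation. Also state the 0.74 SD for the t-test, so that 80% power at 0.25 is not attributed to it.

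In either case, drop the large-sample rule of thumb as a reason for the size, since it says nothing about power. Report between-group differences with 95% confidence intervals, and do not present a non-significant t-test as 80%-powered evidence against a modest benefit.

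Cost: wording only, with no extra patients or assessments. The downside is that the stated detectable effect will look less favourable.

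### A fixed, printed block length of 10 lets a recruiter who can see past allocations deduce an expected 10 of 60 assignments; one 30:30 permuted list would cut this to about 2 at little cost

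*Combined protocol and SAP*

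**What the plan says.** All the relevant text is in the Method section of the combined protocol and SAP.

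- **Sample:** "the total sample size will be 60 participants, with 30 participants in the experimental group and 30 participants in the control group".
- **Study interventions, randomisation:** participants are "divided into 6 blocks of 10 participants each, with random assignment generated by a computer". The split within a block is not given.
- **Study interventions, setting and sampling:** "This study adopts a convenience sampling method", and the trial is run "in the Fifth Department of Internal Medicine ICU". No strata are mentioned, so there is one sequence.
- **Study interventions, recruitment:** "The principal investigator will fully explain the study's purpose and procedures to the patients, and once informed consent is obtained, the recruitment process will begin".
- **Study interventions, order of steps:** the T0 sleep score follows consent, and then "Random assignment will then allocate participants to either the Treat (white noise) group or the Control (standard care) group based on the generated block sequence".
- **Study interventions, white noise group:** "A noise-reducing sleep aid device will be placed at the corner of the bedside cabinet". Controls receive standard care; no sham device is described.

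The document does not say who holds the sequence, how it is concealed, whether the recruiter is kept apart from it, or whether anyone is blinded.

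**The concern.** A fixed block becomes predictable towards its end: once one arm has its full quota, every remaining place in the block is known. Decoding it takes three things: knowing the block length, seeing the earlier allocations, and having some discretion over whom to approach and when. Here the length is printed in the protocol that the recruiter works from. Earlier allocations can be seen on the ward because the device is either present or absent. Convenience sampling leaves room for discretion.

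A recruiter who knows or suspects the next arm could, even without intending to, approach or put off a patient according to how well that patient is expected to sleep. The arms would then differ in case mix for reasons unrelated to white noise, and the outcome is self-reported. Hiding the list does not prevent this, because the prediction comes from the block rule and the visible past allocations. That makes it a matter of the stated design as well as of missing concealment detail.

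**Working it through.** **Inputs.** From the protocol: 60 participants, 30 per arm, 6 blocks of 10. Inferred: 5 per arm in each block. Assumed: the recruiter knows the block length and sees all earlier allocations.

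**The plan's own figure.** 6 × 10 = 60, and 6 × 5 = 30 per arm. This agrees with the Sample paragraph.

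**Certain allocations.** In a balanced block of size 2m, the expected number of final places that are already determined is 2m/(m + 1).

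- Blocks of 10 (m = 5): 10/6 = 1.667 per block; 6 × 1.667 = 10.0 of 60 (16.7%). Enumerating all 252 orderings of a block gives the same value. The last patient of every block is always known, so the minimum is 6. The SD over the trial is 2.2.
- One list of 60 (m = 30): 60/31 = 1.94 in the whole trial.

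**Best guess.** Guessing the arm with fewer patients so far, and tossing a coin at ties, the expected number correct is m + (2^(2m)/C(2m, m) − 1)/2.

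- m = 5: 5 + (1024/252 − 1)/2 = 6.53 of 10, or 39.2 of 60 (65.3%).
- m = 30: 34.37 of 60 (57.3%).

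Chance alone gives 30 of 60.

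**Possible bias.** Assume the recruiter shifts expected sleep score by +h SD when white noise is expected and by −h SD when control is expected. The documents give no value for h; 0.25 and 0.5 are used to show a range.

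- Acting only on certain allocations, the arm difference moves by 2h × 10/60 = 0.333h.
- Guessing throughout, the net number correct is 2 × 39.19 − 60 = 18.38, and the difference moves by 2h × 18.38/60 = 0.613h.
- Guessing throughout with one list, the net is 2 × 34.37 − 60 = 8.74, and the difference moves by 2h × 8.74/60 = 0.291h.

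Type I error below is from simulation of a two-sample t-test on a single post-intervention score, 30 against 30, nominal 5%.

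| Scheme and behaviour | Bias, h = 0.25 | Error | Bias, h = 0.5 | Error |
|---|---|---|---|---|
| Blocks of 10, certain only | 0.08 SD | about 6% | 0.17 SD | about 9% |
| Blocks of 10, every patient guessed | 0.15 SD | about 9% | 0.31 SD | about 18% |
| One list, every patient guessed | 0.07 SD | about 5.5% | 0.15 SD | about 7% |

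**Role of T0.** The simulation was repeated with the shift carried equally in T0 and the post score (assumed correlation 0.5), analysing the change score. With blocks of 10, bias was about 0 and error about 5% at both values of h.

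**Alternative block schemes.** Expected certain allocations of 60, the varied sizes being for a recruiter who knows only the set of possible sizes:

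- fixed 4: 20; fixed 6: 15; fixed 10: 10
- varied 4/6: 3.4; varied 4/6/8: 1.4; varied 6/8/10: 1.0

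The best-guess rate for the varied schemes is 66–69%, no better than the 65% for fixed blocks of 10.

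**The case against.** **The planned analyses use T0.** The Statistical Methods section plans t-tests on pre- and post-intervention differences and a GEE with a group-by-time interaction, and T0 is recorded before assignment. A reader might infer that no planned analysis could remove the bias. The documents do not support that: a lasting difference in sleep, already present at T0, cancels in the change score and in the interaction. This part of the objection stands. Two gaps remain. Selection on expected recovery that T0 does not capture would not cancel, and the t-test wording could also mean separate pre and post comparisons, where the post comparison would be unprotected.

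**The larger bias figures need guessing on every patient.** This also stands. Exploiting only the certain allocations gives roughly half the bias, and the size of the shift is assumed in either case.

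**Discretion may be limited.** The protocol has eligible patients selected on ICU admission, which suggests taking them as they arrive. It does not say consecutively, however, and it names convenience sampling. Allocating after consent and T0 protects the T0 score from knowledge of the actual assignment, but not the earlier decision to approach.

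**Ten is already a long block, and the real gap is concealment.** Smaller fixed blocks would indeed be worse, and the absence of any described concealment is the more basic omission. But concealing the list would leave the 10 deducible allocations in place, while a different list would remove most of them.

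**Conclusion.** The point holds as a cheap improvement of low severity. As written, the plan leaves an expected 10 of 60 allocations deducible and a 65% best-guess rate, against about 1.9 and 57% for a single list. This rests on 5:5 balance within blocks, which is inferred, and on a recruiter who knows the block length and sees every earlier allocation. Both are plausible in one ICU with a visible device, but neither is stated. That the trial is open is likewise an inference, from the device and the lack of any described sham.

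A reader might go further and conclude that recruitment will be biased, or that the type I error will reach 18%. The documents show only the opportunity. The 18% needs an assumed 0.5 SD shift, a guess acted on for every patient, and an analysis that ignores T0. With certain allocations alone, the range is about 0.08 to 0.17 SD and 6 to 9% error on a post-score test. For a lasting shift already in T0, the change-score and interaction analyses are close to unbiased.

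**What to change.** Before enrolment, replace the six fixed blocks of 10 with one computer-generated 30:30 permuted list for all 60 participants. State who holds it, and that this person does not recruit. Keep the list hidden from whoever approaches patients, and release each allocation singly after consent and T0, which is already the stated order.

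Randomly varied, undisclosed block sizes are second best. They cut the certain allocations to about 1 to 3 of 60 but do not eliminate them, and they do not lower the best-guess rate.

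The cost is a regenerated list and a few changed sentences. Exact balance within each successive 10 patients is lost. After 30 patients, the SD of the difference in arm sizes would be 2 × √(30 × 0.25 × 30/59) = 3.9 patients, instead of zero. The final 30:30 split is kept, and no interim analysis is described that would need balance part-way.

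### Baseline significance tests cannot show that randomised arms are comparable, and the sleep comparison adjusts for no baseline covariate; describe baseline instead and prespecify adjustment for T0 and key prognostic factors

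*Combined protocol and SAP*

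**What the plan says.** Under Statistical Methods, Inferential Statistics, the arms are compared before the intervention by significance tests: as an alternative to independent-samples t-tests, "chi-square tests will be used to compare the homogeneity of sleep quality and demographic data between the white noise group and the general care group". No margin is given, and nothing is said about what follows from a significant or a non-significant result. Disease characteristics are to be summarised under Descriptive Statistics, but the homogeneity sentence does not mention them.

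Under Study interventions, the T0 sleep assessment comes first, and then "Random assignment will then allocate participants to either the Treat (white noise) group or the Control (standard care) group". The sample is "divided into 6 blocks of 10 participants each, with random assignment generated by a computer", and the Method section gives the arms "with 30 participants in the experimental group and 30 participants in the control group".

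Two outcome analyses are planned: independent t-tests on pre- and post-intervention sleep quality, and a GEE with group, time and their interaction. Neither names a baseline or prognostic covariate. The Background section describes the contributors to ICU sleep disorder as "including pain, light, and the severity of illness".

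**The concern.** A homogeneity test is normally read as a statement that the arms are comparable. In a randomised trial it cannot support that. The null hypothesis of no population difference is true by design, so a small p-value reports chance, and a large p-value only says that the observed difference fell below a threshold set by the sample size. Whether an imbalance matters depends on its size and on how strongly the variable predicts sleep. The p-value measures neither.

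Two things are at stake. If the tests are non-significant, the plan has nothing further to say about prognostic differences between the arms, and the sleep comparison is unadjusted. If one is significant, the plan is silent, which leaves room to choose covariates after seeing the data.

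**Working it through.** **Inputs.** 30 per arm, 1:1, randomised after T0 (Method; Study interventions). Assumed: two-sided 5% for the baseline tests, equal SDs, no dropout, and covariate-outcome correlation r of 0.3 to 0.6 (0.7 at the top of one range). The plan gives no figure of its own for baseline comparability. Its stated minimum of 58 is not an input here.

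**1. What the t-test flags.** The standard error of a difference in SD units is √(2/30) = 0.258. The critical t on 58 df is 2.002. The smallest flagged difference is 2.002 × 0.258 = 0.517 SD.

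**2. How often an imbalance passes under correct randomisation.**
- Above 0.25 SD: t = 0.25/0.258 = 0.968, two-sided probability 33.7%. The 5.0% that are flagged all lie above 0.517, so 33.7% − 5.0% = 28.7% pass. Simulation with imbalance in population SD units gives 28%.
- At least 0.5 SD: t = 1.936, probability 5.8%, so 5.8% − 5.0% = 0.8% pass.

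**3. Chance flags.** With 10 independent baseline variables (an assumed number), 1 − 0.95^10 = 40% of correctly randomised trials show at least one significant difference.

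**4. Precision lost without adjustment.** For q covariates with joint correlation r with the outcome, the ratio of adjusted to unadjusted standard error is about √(1 − r²) × √(1 + q/(57 − q)). With q = 2 (T0 and age) the second factor is √(1 + 2/55) = 1.018.

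| r | √(1 − r²) | × 1.018 | reduction in SE |
|---|---|---|---|
| 0.3 | 0.954 | 0.971 | 3% |
| 0.5 | 0.866 | 0.882 | 12% |
| 0.6 | 0.800 | 0.814 | 19% |

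Put the other way round, the unadjusted standard error is 3%, 13% and 23% larger (1/0.971, 1/0.882, 1/0.814). Break-even is where √(1 − r²) = 1/1.018, at r = 0.19. It is 0.13 with one covariate and 0.23 with three.

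**5. Conditional bias, no true effect, post-intervention comparison.** About 14% of trials pass the baseline test with an imbalance above 0.25 SD favouring white noise. Their mean imbalance is about 0.35 SD, so the mean bias is 0.35 × r: about 0.11, 0.18 and 0.21 SD at r = 0.3, 0.5 and 0.6. In those trials the unadjusted t-test declares benefit in about 5%, 7% and 8%. Adjustment whatever the p-value returns this to about 2.5%, with bias near zero. With the opposite imbalance the unadjusted rate is below 1%. Over all trials that pass the baseline test it is about 2.0-2.5%, and over all randomisations about 2.5%.

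**6. T0 sleep under the two readings of the t-test.** For a T0 imbalance of D SD and T0-to-post correlation r, a post-only comparison is biased by rD, a change score by (r − 1)D, and ANCOVA by 0. At r = 0.5 the first two are equal and opposite. At r = 0.3 the change score is further off (−0.7D against 0.3D). Unit-SD variances are 2(1 − r) for change and 1 − r² for ANCOVA. At r = 0.3, 0.5 and 0.7 these are 1.4 v 0.91, 1.0 v 0.75 and 0.6 v 0.51. The change-score standard error is therefore about 24%, 15% and 8% larger, before the small degrees-of-freedom cost.

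**The case against.** The best defence is that randomisation already protects the comparison. The unadjusted test keeps its error rate, and the raised false-benefit rates in step 5 exist only in a one-sided, selected 14% of trials. That stands: this is a matter of precision and conditional bias, not of an invalid test.

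Second, the t-test may be a change score, and the GEE interaction uses T0 if T0 is a level of time. Baseline sleep is then not ignored, and a stable factor that shifts T0 and later scores equally cancels. This stands in part. The text leaves the reading open, and subtraction over-corrects a T0 imbalance whenever the correlation is below 1.

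Third, nowhere does the plan say that non-significance certifies the arms or that significance triggers adjustment. That is true. The criticism is that the result is uninformative and its use undefined.

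A reader might go further and infer that because a t-test with 30 per arm misses a 0.5-SD difference 52% of the time, imbalanced arms pass as homogeneous about half the time. The documents do not support this. The 52% is the miss rate for a true population difference, which randomisation rules out. An observed imbalance of 0.5 SD or more passes in only about 0.8% of trials.

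Nor can the imbalance be described as equal to the planned effect. The effect size of 0.25 has no named metric (0.5 SD if it is Cohen's f, 0.25 SD if it is a standardised mean difference), and only the fraction r of an imbalance reaches the outcome.

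**Conclusion.** The point holds as an inexpensive improvement. The baseline tests cannot establish comparability in either direction, and no prognostic covariate is prespecified, although the protocol itself identifies one. The size is moderate: about 28-29% of correctly randomised trials carry an unflagged imbalance above 0.25 SD on a given continuous variable, and the standard error could be about 3% to 19% smaller with adjustment for covariates correlated 0.3 to 0.6 with the outcome. Below about 0.2 there is no gain. Overall type I error is not inflated. Removing the baseline p-values alone would change no result; the benefit comes from the prespecified adjustment.

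These figures rest on 30 analysed per arm, a two-sided 5% baseline test, normal data with equal SDs and the assumed correlations, none of which the documents supply apart from the arm size.

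**What to change.** Replace the homogeneity-test sentence with: baseline characteristics are shown by arm as mean (SD) or n (%), with standardised differences and without p-values; no choice of covariates will rest on a baseline test.

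Make the between-group sleep comparison a GEE (or an ANCOVA) with T1-T3 as the outcomes, adjusted for T0 sleep score and age. Add an illness-severity measure if one is among the recorded disease characteristics; the protocol names none, so this part is conditional. T0 then enters as a covariate and not also as a level of time. Fix the covariates before data lock and keep them whatever imbalance is observed.

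The cost is a few sentences, one to three of the 58 residual degrees of freedom, and the loss of the baseline p-value column. T0 is already collected and age is needed for eligibility. No extra patients or procedures are needed.
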